### 4.2 Scientific Rationale for Study Design

The clinical development of MenACYW conjugate vaccine has started in 2006 with the objective to provide protection against 4 serogroups (A, C, Y, and W) that cause IMD, in all population age

groups, including infant as young as 6 weeks of age and including adults 56 years of age and older.

The initial licensures of this vaccine cover age 2 years and above in the US and age 12 months and above in Europe, Canada, Australia and Brazil, with a single injection. Studies are ongoing to support the extension of indication from 6 weeks of age.

The clinical studies supporting the first licensure were designed to demonstrate the ability of MenACYW conjugate vaccine to safely elicit a robust immune response. Studies were conducted to demonstrate efficacy through the non-inferiority of MenACYW conjugate vaccine compared to licensed meningococcal standard of care vaccines.

According to regulations in Vietnam, local clinical trial data must be generated in order to obtain licensure in this country.

#### 4.3 Justification for Dose

All participants will receive a single dose of MenACYW conjugate vaccine on D01 as per the current/intended indication in this age group for quadrivalent meningococcal conjugate vaccines.

### 4.4 End of Study Definition

A participant is considered to have completed the study if he/she has completed the last visit planned in the SoA.

The end of the study is defined as the date of the last visit of the last participant in the study.

However, for periodic safety reports, the study is considered completed when the clinical study report is finalized.

# 5 Study Population

Prospective approval of protocol deviations to recruitment and enrollment criteria, also known as protocol waivers or exemptions, is not permitted.

#### 5.1 Inclusion Criteria

Participants are eligible for the study only if all of the following criteria are met:

I01: Aged 12 months and above on the day of inclusion

### Adults (aged 18 and above on the day of inclusion):

I02: A female participant is eligible to participate if she is not pregnant or breastfeeding and one of the following conditions applies:

• Is of non-childbearing potential. To be considered of non-childbearing potential, a female must be pre-menarchea or post-menopausal for at least 1 year, or surgically sterile.

#### OR

• Is of childbearing potential and agrees to use an effective contraceptive method or abstinence from at least 4 weeks prior to study intervention administration until at least 4 weeks after study intervention administration.

A female participant of childbearing potential must have a negative highly sensitive pregnancy test (urine) within 1 week before the dose of study intervention.

I03: Informed consent form has been signed and dated

I04: Able to attend all scheduled visits and to comply with all study procedures

### Adolescents (aged 10 to 17 years on the day of inclusionb):

I05: A female participant is eligible to participate if she is not pregnant or breastfeeding and one of the following conditions applies:

• Is of non-childbearing potential. To be considered of non-childbearing potential, a female must be pre-menarchec.

#### OR

• Is of childbearing potential and agrees to use an effective contraceptive method or abstinence from at least 4 weeks prior to study intervention administration until at least 4 weeks after study intervention administration.

A female participant of childbearing potential must have a negative highly sensitive pregnancy test (urine) within 1 week before the dose of study intervention.

Informed consent form has been signed and dated by both the participant (if aged 16 to 18 years) and the parent(s) or another legally acceptable representative and by an independent witness, if required by local regulations

<sup>a Pre-menarche females will declare by themselves that they have not yet started menstruation. If a young female participant reaches menarche during the study, then she is to be considered as a woman of childbearing potential from that time forward

"10 to 17 years" means from the day of the 10th birthday to the day before the 18th birthday

Pre-menarche females will declare by themselves that they have not yet started menstruation. If a young female participant reaches menarche during the study, then she is to be considered as a woman of childbearing potential from that time forward

Assent form has been signed and dated by the participant (assent form required for participants aged 12 to 15 years) or verbal consent has been obtained (for participants aged 10 to 11 years), and informed consent form has been signed and dated by the parent(s) or another legally acceptable representative and by an independent witness, if required by local regulations

I07: Participant and parent/legally acceptable representative are able to attend all scheduled visits and to comply with all study procedures

#### Children (aged 2 to 9 years on the day of inclusiona):

I08: Verbal consent has been obtained (for participants aged 7 to 9 years), and informed consent form has been signed and dated by the parent(s) or another legally acceptable representative and by an independent witness, if required by local regulations

I09: Participant and parent/legally acceptable representative are able to attend all scheduled visits and to comply with all study procedures

### Toddlers (aged 12 to 23 months on the day of inclusionb)

Informed consent form has been signed and dated by the parent(s) or other legally acceptable representative and by an independent witness if required by local regulations

I11: Participant and parent/legally acceptable representative are able to attend all scheduled visits and to comply with all study procedures

#### 5.2 Exclusion Criteria

Participants are not eligible for the study if any of the following criteria are met:

Adults (aged 18 years and above), Adolescents (aged 10 to 17 years), Children (aged 2 to 9 years) and Toddlers (aged 12 to 23 months)

E01: Participation at the time of study enrollment (or in the 4 weeks preceding the study intervention administration) or planned participation during the present trial period in another clinical study investigating a vaccine, drug, medical device, or medical procedure

E02: Receipt of any vaccine in the 4 weeks preceding the study intervention administration or planned receipt of any vaccine in the 4 weeks following study intervention administration except for influenza vaccination, which may be received at least 2

<sup>a "2 to 9 years" means from the day of the 2nd birthday to the day before the 10th birthday

b "12 to 23 months" means from the 12th month after birth to the day before the 25th month after birth

- weeks before or after study vaccine. This exception includes monovalent pandemic influenza vaccines and multivalent influenza vaccines.
- E03: Previous vaccination against meningococcal disease with either the study vaccine or another vaccine (ie, polysaccharide, or conjugate meningococcal vaccine containing serogroups A, C, W, or Y; or meningococcal B serogroup-containing vaccine)
- E04: Receipt of immune globulins, blood or blood-derived products in the past 3 months
- E05: History of any *N. meningitidis* infection, confirmed either clinically, serologically, or microbiologically
- E06: At high risk for meningococcal disease during the study (specifically but not limited to participants with persistent complement deficiency, with anatomic or functional asplenia, or participants traveling to countries with high endemic or epidemic disease)
- E07: Known systemic hypersensitivity to any of the study intervention components, or history of a life-threatening reaction to the study intervention used in the study or to a product containing any of the same substancesa
- E08: Personal history of Guillain-Barré syndrome
- E09: Bleeding disorder, or receipt of anticoagulants in the 3 weeks preceding inclusion, contraindicating intramuscular injection
- E10: Deprived of freedom by an administrative or court order, or in an emergency setting, or hospitalized involuntarily
- E11: Chronic illness that, in the opinion of the Investigator, is at a stage where it might interfere with study conduct or completionb
- E12: Moderate or severe acute illness/infection (according to Investigator judgment) on the day of vaccination or febrile illness (axillary temperature ≥ 37.5°C) or hypothermia (axillary temperature ≤ 35.5°C) on the day of vaccination. A prospective participant should not be included in the study until the condition has resolved or the febrile event has subsided
- E13: Receipt of oral or injectable antibiotic therapy within 72 hours prior to the first blood draw

### Adults (aged 18 years and above) and Adolescents (aged 10 to 17 years)

E14: Known or suspected congenital or acquired immunodeficiency; or receipt of immunosuppressive therapy, such as anti-cancer chemotherapy or radiation therapy, within the preceding 6 months; or long-term systemic corticosteroid therapy

<sup>a The components of MenACYW conjugate vaccine are listed in Section 6.1, and in Section 3 of the IB.

Chronic illness may include, but is not limited to, cardiac disorders, renal disorders, auto-immune disorders, diabetes, psychiatric disorders or chronic infection

- (prednisone or equivalent for more than 2 consecutive weeks within the past 3 months)
- E15: Personal history of an Arthus-like reaction after vaccination with a tetanus toxoid-containing vaccine within at least 10 years of the proposed study vaccination
- E16: Self-reported thrombocytopenia, contraindicating intramuscular injection
- E17: Alcohol, prescription drug, or substance abuse that, in the opinion of the Investigator, might interfere with the study conduct or completion
- E18: Identified as an Investigator or employee of the Investigator or study center with direct involvement in the proposed study, or identified as an immediate family member (ie, parent, spouse, natural or adopted child) of the Investigator or employee with direct involvement in the proposed study

### Children (aged 2 to 9 years)

- E19: Known or suspected congenital or acquired immunodeficiency; or receipt of immunosuppressive therapy, such as anti-cancer chemotherapy or radiation therapy, within the preceding 6 months; or long-term systemic corticosteroid therapy (prednisone or equivalent for more than 2 consecutive weeks within the past 3 months)
- E20: Personal history of an Arthus-like reaction after vaccination with a tetanus toxoid-containing vaccine
- E21: Thrombocytopenia as reported by the parent/legally acceptable representative, or suspected thrombocytopenia contraindicating intramuscular injection
- E22: Identified as a natural or adopted child of the Investigator or employee with direct involvement in the proposed study

### Toddlers (aged 12 to 23 months)

- E23: Known or suspected congenital or acquired immunodeficiency; or receipt of immunosuppressive therapy, such as anti-cancer chemotherapy or radiation therapy, within the preceding 6 months; or long-term systemic corticosteroid therapy (prednisone or equivalent for more than 2 consecutive weeks since birth)
- E24: Personal history of an Arthus-like reaction after vaccination with a tetanus toxoid-containing vaccine
- E25: Thrombocytopenia as reported by the parent/legally acceptable representative, or suspected thrombocytopenia contraindicating intramuscular injection
- E26: Identified as a natural or adopted child of the Investigator or employee with direct involvement in the proposed study

If the participant has a primary physician who is not the Investigator, the site is recommended to

contact this physician with the participant's consent to inform him/her of the participant's participation in the study. In addition, the site may ask this primary physician to verify exclusion criteria relating to previous therapies, such as receipt of blood products or previous vaccines.

### **5.3** Lifestyle Considerations

No other restrictions than the ones listed in the exclusion criteria or in the contraindications for the subsequent blood sample (on Visit 2) are required.

#### 5.4 Screen Failures

Screen failures are defined as participants who consent to participate in the clinical study but are not subsequently assigned to study intervention. Screening information is recorded in the source documents.

### 5.5 Criterion for Temporarily Delaying Enrollment

The reactogenicity of any of the COVID-19 vaccines available to date will occur during the first few days post-immunization. As immunogenicity interactions with other vaccines have not been studied, if the first dose of a COVID-19 vaccination is received before the participant is enrolled in the study, it is recommended to postpone enrollment at least 4 weeks after the last COVID-19 vaccine dose.

### 6 Study Intervention and Concomitant Therapy

Study intervention is defined as any investigational intervention(s), marketed product(s), placebo, or medical device(s) intended to be administered to a study participant according to the study protocol.

Note: Vaccines or products administered outside of study protocol are not considered as study interventions and are reported in the CRF as reportable medications (see Section 6.8). Study procedures (eg, blood sampling) are also not considered as study interventions.

### 6.1 Study Intervention Administered

Study interventions are described in Table 6.1.

**Table 6.1: Identity of study intervention** 

Intervention Name	MenACYW conjugate vaccine: Meningococcal Polysaccharide	
	(Serogroups A, C, W, and Y) Tetanus Toxoid Conjugate Vaccine	
	(Sanofi Pasteur Inc., Swiftwater, PA, USA)	
Use	Investigational	
IMP and NIMP	IMP	
Type	Vaccine	
Dose Formulation	Liquid solution	
Unit Dose Strength(s)	Each dose of MenACYW conjugate vaccine contains the following components:  Meningococcal capsular polysaccharides:  • Serogroup A*: 10 μg  • Serogroup C*: 10 μg  • Serogroup Y*: 10 μg  • Serogroup W*: 10 μg  * Conjugated to tetanus toxoid protein carrier: 55 μg**	
	**Tetanus toxoid protein quantity is approximate and dependent on the polysaccharide-to-protein ratio for the conjugates used in each	
E : : (/D)	formulation	
Excipients/Diluent	Sodium acetate buffered saline solution	
Dosage Level	0.5 mL per dose	
Number of Doses / Dosing	1 dose	
Interval		
Route of Administration	Intramuscular injection	
Site of Administration	Anterolateral area of the thigh or deltoid muscle	
Sourcing	Provided by the Sponsor	
Packaging and Labeling	MenACYW conjugate vaccine (single-dose vial) will be supplied with investigational labeling and packaging according to national regulations. Each single dose of study interventions will be identified by a unique number on the detachable label and on the outer carton label. The detachable label is for the sites to attach to the source documents. See the Operating Guidelines for additional label detail.	
Current/Former Name or	MenQuadfi™	
Alias		
Batch Number	TBD	
Storage Conditions	Study interventions will be stored in a refrigerator at a temperature	
	ranging from +2°C to +8°C. The study interventions must not be frozen.	

IMP: investigational medicinal product; NIMP: non-investigational medicinal product; TBD: to be determined

### 6.2 Preparation/Handling/Storage/Accountability

Detailed guidance and information are provided in the Operating Guidelines.

- 1) The Investigator or designee must confirm appropriate temperature conditions have been maintained during transit for all study intervention received and any discrepancies are reported and resolved before use of the study intervention.
- 2) Only participants enrolled in the study may receive study intervention and only authorized site staff may supply or administer study intervention. All study intervention must be stored in a secure, environmentally controlled, and monitored (manual or automated) area in accordance with the labeled storage conditions with access limited to the Investigator and authorized site staff.
- 3) The Investigator, institution, or the head of the medical institution (where applicable) is responsible for study intervention accountability, reconciliation, and record maintenance (ie, receipt, reconciliation, and final disposition records).
- 4) Further guidance and information for the final disposition of unused study interventions are provided in the Operating Guidelines.

### 6.3 Measures to Minimize Bias: Randomization and Blinding

#### 6.3.1 Randomization and Allocation Procedures

Participants will not be randomized.

#### **6.3.2** Blinding and Code-breaking Procedures

This is a single-arm study that is not blinded.

### **6.4** Study Intervention Compliance

The following measures will ensure that the study intervention is administered as planned (see Table 6.1), and that any non-compliance is documented so that it can be accounted for in the data analyses:

- All study interventions will be administered by qualified and trained study personnel
- The person in charge of study intervention management at the site will maintain accountability records of study intervention delivery to the study site, study intervention inventory at the site, dose(s) given to each participant, and unused or wasted doses

#### 6.5 Dose Modification

Not applicable.

### 6.6 Continued Access to Study Intervention After the End of the Study

Not applicable.

#### **6.7** Treatment of Overdose

Since the study intervention is administered by a health care professional, it is unlikely that overdose by injection occurs.

However, in the event of an overdose, the Investigator should:

- 1) Contact the Medical Monitor immediately
- 2) Closely monitor the participant for any AE/SAE
- 3) Document the quantity of the excess of the overdose in the source documents

### 6.8 Concomitant Therapy

At the time of enrollment, ongoing medications and other therapies (eg, blood products) should be recorded in the source document as well as new medications prescribed for new medical conditions/AEs during study participation.

Documentation in the CRF of ongoing concomitant medication(s) will be limited to specific categories of medication(s) of interest beginning on the day of vaccination. This may include medications of interest that were started prior to the day of vaccination.

Reportable medications include medications that may affect the interpretation of safety data (eg, an antipyretic or analgesic that could have reduced the intensity or frequency of an adverse event) or may interfere with the development or measurement of the immune response (eg, the use of immune-suppressors, immune-modulators, or some antibiotics that can affect certain bioassays). Some medications such as steroids can affect both the evaluation of the safety and the immune response to a vaccine.

This may include medications of interest that were started prior to the day of vaccination, and even stopped prior to enrollment if there is a reasonable possibility that they may have an impact on safety and/or immune assessment during study participation.

The following reportable medications are defined:

• Category 1: medications impacting or that may have an impact on the evaluation of the safety (eg, antipyretics, analgesics, and non-steroidal anti-inflammatory drugs [NSAIDs], systemic steroids/corticosteroids [therapy duration less than 2 weeks] and other immune-modulators) Category 1 medications do not define the per-protocol analysis set (PPAS).

Note: Topical analgesics should NOT be applied at the injection site of study intervention; however, if they are applied inadvertently, they should be recorded.

Note: Topical steroids (inhaled, optic, ophthalmic, nasal, etc.) should not be captured or reported.

Category 1 medications will be reported in the CRF from the day of vaccination to the end of the solicited and unsolicited follow-up period.

- Category 2: medications impacting or that may have an impact on the immune response and used to define the PPAS; for example:
  - Flu vaccines administered 14 days (2 weeks) pre or post study intervention administration, including the day of the study vaccination visit.
  - Any vaccine other than the study vaccine and flu vaccines within the 4 weeks
    preceding or after the study vaccination, including the day of the study vaccination
    visit.
  - Immune globulins, blood or blood-derived products: used in the 3 months preceding the first blood draw and up to the last blood draw
  - Immunosuppressive therapy such as immune-suppressors, immune-modulators with immunosuppressive properties, long-term systemic corticosteroids therapy (prednisone or equivalent for more than 2 consecutive weeks) used in the 3 months preceding the study vaccination and up to the last blood draw, anti-cancer chemotherapy, anti-proliferative drugs such as deoxyribonucleic acid (DNA) synthesis inhibitors, or radiation therapy: used in the 6 months preceding the study vaccination, and up to the last blood draw

Category 2 medications will be reported in the CRF according to the collection period detailed above up to the last blood draw.

Category 3: medications impacting or that may have an impact on both the safety and the
immune response: systemic (oral or injectable) antibiotics, received within 72 hours
preceding each visit for blood draw related to investigational medicinal product (IMP)
assessment (MenACYW conjugate vaccine) and used to define the PPAS, as they may
interfere with bioassays used for antibody testing when taken before a blood draw

Category 3 medications will be reported in the CRF for the period of 3 days (72 hours) before each blood draw.

Note: Topical antibiotics (inhaled, optic, ophthalmic, nasal, etc.) should not be captured or reported.

Reportable medications (Category 1, 2, and 3) will be collected in the source document from the day of vaccination to the end of the study and in the CRF as per the instructions given below for each category.

The information reported in the CRF for each reported medication will be limited to:

- Trade name
- Rationale for the origin of prescription: Whether it was a prophylactic a medication?
   Prophylactic medications will be recorded in the Action Taken section of the AE collection tables
- Medication category (1, 2, or 3)
- Start and stop dates

\_

<sup>a Medication prescribed for preventing AE occurrence (eg, paracetamol to reduce the risk of fever)

Dosage and administration route, homeopathic medication, topical and inhaled steroids, as well as topical, ophthalmic, and ear treatments will not be recorded (except topical analgesics applied at the injection site of study intervention).

If the participant has received medications other than those listed in Categories 1, 2, and 3, the detailed information will be collected in the source documents only.

Medications given in response to an AE will be captured in the "Action Taken" section of the AE CRF only. No details will be recorded in the concomitant medication CRF unless the medication(s) received belongs to one of the pre-listed categories. Medications will not be coded.

#### 6.8.1 Rescue Medicine

Appropriate medical equipment and emergency medications, including epinephrine (1:1000), must be available at the study site in the event of an anaphylactic, vasovagal, or other immediate allergic reaction.

#### 6.8.2 Coronavirus Disease 2019 Vaccine

If after study initiation coronavirus disease 2019 (COVID-19) vaccines become available for the population under study, the highest priority will be that study participants get their immunizations as per country recommendations.

Refer to Section 5.5 for the criterion for temporarily delaying enrollment in case of receipt of COVID-19 vaccine.

If a COVID-19 vaccine dose is received during one IMP solicited reactogenicity period it would not be possible to differentiate systemic reactions between the two. Likewise, if the vaccine is received between an IMP dose and the collection of blood, it will not be possible (at this point) to rule out an immunogenicity interaction. Therefore, in any of those two situations it is recommended that the participant be pulled out of the per protocol (PP) population but should continue in the trial within the intent-to-treat (ITT) population.

If the above observations would not apply, the participant could continue as PP.

The kind of COVID-19 vaccine received (including tradename) and the date time of its administration(s) should be documented in the concomitant medications CRF.

Wherever possible the site of injection of the IMP should be in the limb separate from the limb in which COVID-19 vaccine is administered (if it has already been administered). Likewise, and if on the control of the study site, any COVID-19 vaccine scheduled to be received after administration of the IMP should not be received in the same limb as the IMP. Where it is not possible to have the IMP and COVID-19 vaccine administered in separate limbs, a distance of at least 3.8 to 5.1 centimeters (1.5 to 2 inches) should be maintained between the two administration sites.

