## 9.3 Analysis Sets

The following populations are defined for immunogenicity and safety analyses:

Analysis Set	Description
Full analysis set	Participants who received the study vaccine and had a valid post-vaccination
(FAS)	serology result.
Per-protocol analysis set (PPAS)	
 
Subset of the FAS. Participants presenting with at least one of the following relevant protocol deviations will be excluded from the PPAS:
 
Participants did not meet all protocol-specified inclusion criteria or met at least one of the protocol-specified exclusion criteria
 

	Participant did not receive vaccine
	
 
Preparation and / or administration of vaccine was not done as per-protocol
 
Participants did not provide the post-dose serology sample at Visit 2 in the proper time window or a post-dose serology sample was not drawn
 
Participants received a category 2 or 3 protocol-prohibited therapy / medication / vaccine
 

	• Participants had other protocol violations that affected the participant's immune response, as determined by the clinical team before locking the database.
	In addition to the reasons listed above, participants will also be excluded from the PPAS if their Visit 2 serology sample did not produce a valid test result.
	In the event of a local or national immunization program with a pandemic
	COVID-19 vaccine, participants who receive COVID-19 vaccine between an
	IMP dose and the collection of blood will not be withdrawn from the study, but will be excluded from PPAS.
Safety analysis set (SafAS)	Participants who have received the study vaccine and have any safety data available.

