#### 9.4.2 Immunogenicity Endpoint

No statistical hypotheses will be tested. Descriptive statistics will be provided for the antibody titers against meningococcal serogroups A, C, W, and Y by using hSBA before and 30 days after a single dose of meningococcal conjugate vaccine.

All immunogenicity analyses will be performed on the PPAS. Additional immunogenicity analyses will be performed for exploratory purposes on the FAS.

In general, categorical variables will be summarized and presented by frequency counts, percentages, and CIs. The 95% CIs of point estimates will be calculated using the normal approximation for quantitative data and the exact binomial distribution (Clopper-Pearson method) for percentages (16). For GMTs, 95% CIs of point estimates will be calculated using normal approximation assuming they are log10-normally distributed.

Descriptive analyses of antibody responses to A, C, W, and Y serogroups using hSBA will include but not be limited to:

- GMTs and 95% CI.
- Titer distribution and reverse cumulative distribution curves (RCDCs)
- Percentage of participants with titers ≥ 4-fold rise from pre-vaccination to post-vaccination, and 95% CI
- Percentage of participants with hSBA titers  $\geq 1:4$  and  $\geq 1:8$ , and 95% CI
- Percentage of participants with hSBA vaccine seroresponse, and 95% CI
   Note: hSBA vaccine seroresponse for serogroups A, C, W, and Y is defined as:
  - For a participant with a pre-vaccination titer < 1:8, the post-vaccination titer must be > 1:16
  - $\circ$  For a participant with a pre-vaccination titer  $\geq 1:8$ , the post-vaccination titer must be at least 4-fold greater than the pre-vaccination titer

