#### 9.4.3 Safety Endpoints

No statistical hypotheses will be tested.

Safety results will be described for participants in the study. The main parameters for the safety endpoints will be described by 95% CIs (based on the Clopper-Pearson method).

Depending on the items, the endpoints recorded or derived could include: nature (Medical Dictionary for Regulatory Activities [MedDRA] preferred term), time of onset, duration/number of days of occurrence, intensity, relationship to the vaccine, whether the AE led to early termination from the study, outcome, and seriousness criterion.

All safety analyses will be performed on the SafAS.

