3.4.4.1.2 Causal Relationship

By convention, all events reported at the injection site (either solicited or unsolicited) will be considered as related to the administered product and then referred to as reactions. In a same way, all solicited systemic events pre-listed in the CRF are also considered as related to vaccination and will be considered as reactions.

- For unsolicited systemic AE, missing relationship will be considered as related to study vaccine at the time of analysis.
- The missing relationship to study procedures for SAEs will not be imputed.

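### Removal from the per-protocol set does not deal with the unattributable systemic reactions that protocol 6.8.2 describes, because the main safety analysis does not use that set

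*Protocol*

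**What the plan says.** Protocol 6.8.2 describes two situations. If a COVID-19 vaccine falls in the solicited reactogenicity period, "it would not be possible to differentiate systemic reactions between the two". If it falls between the study dose and the blood draw, an effect on the immune response cannot be ruled out. One remedy covers both: "Therefore, in any of those two situations it is recommended that the participant be pulled out of the per protocol (PP) population". The participant is to continue in an ITT population.

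The sets are defined elsewhere. Protocol 9.3 says that participants given a COVID-19 vaccine between the study dose and the blood draw "will be excluded from PPAS". Protocol 9.4.2 gives that set its use: "All immunogenicity analyses will be performed on the PPAS". The SafAS is defined as "Participants who have received the study vaccine and have any safety data available", and protocol 9.4.3 states "All safety analyses will be performed on the SafAS"; SAP 3.4.3 says the same.

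On causality, SAP 3.4.4.1.2 says that "all solicited systemic events pre-listed in the CRF are also considered as related to vaccination". Protocol 10.2.3 has the same convention and asks for no investigator opinion on these events.

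**The concern.** The first situation in 6.8.2 is about attributing safety events, but the remedy acts on an immunogenicity set. A participant given a COVID-19 vaccine on, say, D03 leaves the PPAS and stays in the SafAS. Fever, headache, malaise or myalgia on the following days is then tabulated as a reaction to the study vaccine.

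The study has no control arm, so nothing else in the tables separates the two vaccines. What is at stake is whether the solicited systemic rates can be read as the reactogenicity of the study vaccine alone, and whether any handling of such cases is settled before the data are seen.

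**Working it through.** The plan gives no figure on this point, so the check is mainly a tracing of rules.

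**Step 1: does PPAS removal change any main safety result?**
- The PPAS is a subset of the FAS, which requires a valid post-vaccination serology result (protocol 9.3, SAP 3.3). It is an immunogenicity set.
- The SafAS requires only vaccination and some safety data. Neither document adds an exclusion for another vaccine.
- Main safety tables use the SafAS only (protocol 9.4.3, SAP 3.4.3).
- Result: no change.

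**Step 2: does the first situation add anything to the second?** A dose given after the study vaccine on D01 to D08 also precedes the Visit 2 sample on D31 (+14 days). It therefore already triggers PPAS exclusion under the blood-draw rule. Naming PP removal for the reactogenicity situation as well has no further effect.

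**Step 3: is there another rule?**
- The derivations for solicited reactions in SAP 4.2.1.1 contain no flag, censoring or sensitivity analysis for a second vaccine.
- Protocol 9.4.1 plans a summary of safety endpoints in participants impacted by COVID-19, but only if they exceed 10%. Impact there means a major or critical deviation due to COVID-19, or non-completion due to it. It adds a summary and leaves the main table as it is. The SAP does not carry it.
- SAP 4.1 plans age-subgroup analyses of immunogenicity and safety for all analysis sets. Read literally, that puts some safety output on the PPAS, which conflicts with SAP 3.4.3. Even so, the main tables would be unchanged.
- Protocol 6.8.2 also asks for separate limbs. That bears on injection site reactions, not systemic ones.

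**Step 4: possible size.** The documents give neither the number affected (k) nor the excess reaction rate after the other vaccine (e). Both are assumptions here, and N = 446 assumes that all enrolled participants (protocol 9.2) enter the SafAS.

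Inflation of the rate = (k / 446) × e

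| k | k / 446 | e = 20 points | e = 60 points |
|---|---|---|---|
| 0 | 0% | 0 | 0 |
| 4 | 0.9% | 0.18 | 0.54 |
| 22 | 4.9% | 0.99 | 2.96 |
| 44 | 9.9% | 1.97 | 5.92 |

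The last row is the largest count that could not pass the 10% trigger in protocol 9.4.1 (0.10 × 446 = 44.6), even if every such participant counted as impacted. For scale, the Clopper-Pearson 95% half-width at N = 446 is 3.8 points for a rate of 20%, 4.4 for 30% and 4.7 for 50%.

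**The case against.** The strongest reply is that overlap should be rare and that keeping these participants in the safety set is right.

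- E02 excludes anyone planning to receive another vaccine in the four weeks after the study dose, with influenza vaccine allowed only at least two weeks away.
- Protocol 5.5 recommends delaying enrollment after a COVID-19 dose.
- SAP section 5 says the study started only once COVID-19 was no longer a pandemic.
- Counting every event can only raise reported reactogenicity; it cannot hide harm.
- No hypothesis is tested.

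Most of this stands. It limits the size, fixes the direction and supports the SafAS as the main set. It does not close the gap. E02 covers planned vaccination only, while 6.8.2 gives national COVID-19 immunization the highest priority after study start and so expects some overlap. A later start makes a count of zero plausible but does not establish it.

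A reader might go further in three ways that the documents do not support.

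- **That the reported rates are materially inflated, above all in the small adult subgroups.** Nothing says how many participants were co-vaccinated or at what ages. In a subgroup at its minimum of 20, one reaction is 1/20 = 5 points, but that is a shift only if the participant would not otherwise have reacted. In expectation it is e/20, or 1 to 3 points for e of 20 to 60 points.
- **That no safety output could ever use the PPAS.** The wording of SAP 4.1 leaves that open.
- **That the SAP, by omitting the protocol's COVID-19 sentence from its PPAS definition, lets these participants back into the PPAS.** For a dose on D01 to D08, the Category 2 rule on vaccines within four weeks still removes them.

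**Conclusion.** The mismatch is real. Protocol 6.8.2 names a safety problem and answers it with a set change that the main safety analysis never sees, while the causality convention assigns the events to the study vaccine. The ITT population that it names is defined in neither document.

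The practical effect is unknown and may be nil. The range of 0 to 5.9 points rests wholly on assumed counts and excess rates. Near 1% affected, it is far inside the sampling error; only the most extreme combination shown exceeds the half-widths above. Any bias is upward. The case for a change rests on a rule that misses its stated purpose and is cheap to repair, not on a demonstrated distortion.

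The protocol states non-attributability for COVID-19 vaccines only. Extending the handling to other non-study vaccines given on D01 to D08 follows from the same logic but goes beyond its text.

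**What to change.** **SAP 3.4.3 and 4.2.1.1**
- Keep the SafAS table as the main result.
- From the vaccine name and date on the concomitant medication CRF, flag participants given a COVID-19 vaccine, or any other non-study vaccine, on D01 to D08.
- If there are none, say so in one line. If there are any, repeat the solicited systemic reaction table without them, and list their reactions with the date of the other vaccine.
- Do not merely set their later diary days to missing. Under SAP 4.2.1.1.3 a participant with any non-missing presence stays in the analysis, so these participants would usually remain in the denominator with a shorter window, which biases the rate downward.

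**SAP 4.1:** reconcile the reference to all analysis sets with SAP 3.4.3.

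**Protocol 6.8.2:** separate the two situations, with PPAS removal for the blood-draw situation and the supportive analysis for the reactogenicity situation. Use the names FAS, PPAS and SafAS.

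**Cost:** one flag, one table and one listing, possibly empty, with a slightly smaller denominator in the supportive table. No new data are needed, provided the concomitant medication CRF was completed as 6.8.2 requires. Medications are not coded (protocol 6.8), so the flag needs a manual read of trade names.
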